#### *7.1.10.2 Secondary outcome measures*

At baseline assessment participant demographics will be collected as well as a history of use of acamprosate, other relapse prevention medication use, and previous medically assisted

detoxification using a medical history checklist devised specifically for the trial. The substance use section of the Alcohol, Smoking and Substance Involvement Screening Test- Lite (ASSIST-Lite;(13)) will be administered to obtain a history of any substance use.

Severity of dependence will be measured at the initial screening assessment and at 6 and 12 month follow-up using the Severity of Alcohol Dependence Questionnaire (SADQ) (85). The SADQ is a 20-item self-complete questionnaire containing items representing five domains of the alcohol dependence syndrome: (i) physical withdrawal signs (ii) psychological withdrawal signs (iii) withdrawal relief drinking (iv) tolerance (v) reinstatement following a period of abstinence.

Alcohol consumption will be measured using the Time Line Follow Back (TLFB) Form 90 (86), administered at initial screening assessment and at 6 and 12 month follow-up after initiation of acamprosate. Percentage days abstinent, units of alcohol per drinking day (1 UK unit = 8g alcohol), time to first alcoholic drink, relapse to any drinking and relapse to heavy drinking (8+/6+ units for males/females on a single occasion) will be computed.

Participants' beliefs about medications will be assessed using the Beliefs about Medications Questionnaire (BMQ; (87)). The BMQ assesses an individual's beliefs about medication specific to them and their health, as well as their general beliefs about medication. This questionnaire will be administered at initial screening assessment and at 6 month follow-up. The measure will be used to evaluate the impact of MM on beliefs and concerns about medication and the association with adherence to acamprosate.

Participants will be asked to rate their therapeutic relationship with the care provider monitoring their medication adherence at each follow up point using the STAR rating scale (88). Therapeutic relationship (or alliance) has been found to predict clinical outcome across a range of mental disorders (89) including alcohol dependence (90). This will be used as an additional process measure to assess the impact of therapeutic relationship on medication adherence and clinical outcome.

Alcohol related problems will be assessed at initial screening assessment and then at 6 and 12 month follow-up, using the Alcohol Problems Questionnaire (APQ; (4)). The APQ is a 46-item questionnaire assessing potential problems with psychological, physical, social, legal, employment, relationships and parenting that may be experienced due to alcohol. The Alcohol Urge Questionnaire (AUQ) (91) assesses current urge for alcohol using eight items which cover three factors: desire for a drink (4 items); expectation of positive effect from drinking (2 items); and inability to avoid drinking if alcohol was available (2 items). This questionnaire will be administered at initial screening assessment and at 6 and 12 month follow-up.

Health related quality of life will be measured using the EQ-5D-5L and participants' use of services will be measured using the Alcohol and Drug Adapted Adult Service Use Schedule (AD-SUS). These measures will be used to assess the cost-effectiveness of MM and MM+CM compared to SS. These measures will be collected at baseline assessment and at 6 and 12 month follow-up.

Participants will be asked at each bi-monthly research visit whether they have experienced any side effects from the medication. In addition, reasons for non-adherence will be recorded.

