## 1. Summary of research

Design: 3-arm, prospective, pragmatic, randomised controlled, parallel group clinical trial of strategies to enhance adherence to prescribed acamprosate for alcohol dependence. Standard support (SS), SS with adjunctive medication management (SS+MM), SS and MM with adjunctive contingency management (SS+MM+CM). Outcome assessment will be at 6 and 12 months post randomisation.

Setting: Specialist community alcohol treatment services, community pharmacies local to participants and a central telephone support service.

Population: Abstinent alcohol dependent adults, suitable for prescription of acamprosate, willing and able to provide informed consent.

Inclusion criteria: Aged  $\geq 18$ , ICD-10 alcohol dependence, currently abstinent from alcohol, commencing a prescription for acamprosate.

Exclusion criteria: Severe physical/mental illness identified by the treating clinicians, participation in another trial, unable to adequately understand verbal English, current dependence on an illicit substance.

Health technologies: MM provided by pharmacists via a central telephone support service (weekly for 6 weeks and then fortnightly for 6 weeks and then 4-weekly up to 24 weeks). MM plus CM: Small incentives (vouchers) will be provided to reinforce adherence to telephone support, ranging from £2 to £10 for each MM session completed, with a total value of up to £120 for completing all support sessions.

Primary outcome measure: Proportion of prescribed medication taken assessed using Medication Events Monitoring System (MEMS) and cross-verified using pill count and self-report at 6 months post randomisation.

Secondary outcomes: Proportion of prescribed medication taken, estimated by self-report at 12 months post-randomisation. Total alcohol consumed, drinks per drinking day, percent days abstinent in standard drinks (1 standard drink = 8g ethanol) in the previous 90 days derived using the Time Line Follow Back Form 90. Time to first drink, relapse to any drinking and relapse to heavy drinking (8+/6+ UK units for males/females on a single occasion) derived from self-report. Alcohol related problems (Alcohol Problems Questionnaire), alcohol craving (Alcohol Urge Questionnaire) and severity of alcohol dependence. Measured at baseline, 6 and 12 months post-randomisation.

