#### 7.1.1 Design and theoretical/conceptual framework

The study will be a 3-arm, pragmatic, randomised controlled, parallel group clinical trial. Each participant will be prescribed acamprosate as soon as possible after alcohol abstinence is achieved for a minimum duration of 24 weeks. Follow-up contacts with the research team will take place 6 (+30 days) and 12 (+60 days) months post randomisation. Participants will collect their medication monthly from the community pharmacy, which will be dispensed from designated pharmacies in bottles with MEMSCaps. Consented participants will be randomised (in the order of 2:1:1) to receive;

- SS consisting of monthly pick up of prescribed acamprosate from the community pharmacy and monthly follow-up with their specialist alcohol team for three months followed by monthly follow up with their GP for three months; or
- SS+ MM once a week for the first 6 weeks, reducing to once a fortnight for the following 6 weeks, and then monthly for 3 months, delivered by telephone by a trained pharmacist from a central telephone support service; or
- SS+MM+CM which will include incentivisation for completion of each of the telephone MM support sessions, with the pharmacist.

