#### 7.1.10 Data collection

Table 1 outlines the study outcome measures and timing of their administration during the study. Research and personal data will be collected using electronic data capture, specifically designed for this research study by Codeface Ltd, using a laptop computer. Laptop computers will be password protected. Data will be entered and saved on a secure server with a 256bit encryption, no data will be saved directly onto the laptop computer. Research data will be anonymised by assigning

each participant a unique ID number, personal data will be stored separately to the research data to maintain participant anonymity.

All of the study interventions will be audio recorded and a proportion will be reviewed by the research team to check the fidelity of the delivery of the intervention and inform further training. Audio files will be stored on a secure server with restricted access through password protected computers. Consent to take part in the research will be captured using an electronic consent form overseen by the researcher.

Table 1: Trial outcome measures, timing of administration and duration of participant completed questionnaires

		Baseline	Bi-Monthly visit (months 1 to 6)	6 month follow-up	12 month follow-up
CIDI	Diagnosis of alcohol dependence				
ASSIST	Psychoactive drug misuse				
SADQ	Severity of alcohol dependence				
AUQ	Current craving for alcohol				
APQ	Presence of alcohol related problems				
TLFB	Percentage of days abstinent and Units of alcohol per drinking day Time to first alcoholic drink Time to relapse to any drinking Time to relapse to heavy drinking.				

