### 7.2.4 Data analysis

In the main trial the primary outcome measure is percent prescribed medication taken at 24 weeks post-randomisation assessed using a triangulation method. After checking for distributional assumptions and employing necessary transformations, an initial multiple analysis of covariance will be undertaken using a mixed model approach addressing the observed differences between SS versus SS+MM versus SS+MM+CM. If this analysis provides evidence of effect a second analysis of covariance will explore the differences of SS versus SS+MM and SS versus SS+MM+CM. Covariates included in the analysis will include stratification variables, gender and body weight (<60kg or 60+ kg). Mean differences between the groups will be presented with associated 95% confidence intervals. Multiple imputation will be employed to address the nature of missing data and sensitivity analysis will address the influence of missing data on the observed outcome. Secondary analysis will address drinking outcomes at 6 and 12 months using appropriate modelling approaches and these will be adjusted for known confounders; SADQ, site, age and gender. Time to relapse and relapse to heavy drinking will be assessed using survival analysis. Further secondary analyses will explore adherence data at 12 months. We will explore the association between adherence and drinking outcomes using a linear regression adjusted for known confounders and include an adherence\*allocation interaction term. As with most trials the analysis plan will be refined throughout the course of the study and the final analysis plan prepared and agreed by the research team and Trial Steering Committee.

Further analysis will be conducted to identify interactions between variables, including ratings of therapeutic relationship, and fidelity of MM and CM delivery, on clinical and adherence outcomes. The analysis will be governed by an explicit data analysis plan agreed in advance by the Trial Steering Committee.

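### Time to first drink and relapse rest on a drinking form given only at months 6 and 12; if its 90-day look-back applies to them, about half the year goes unasked

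*Protocol*

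**What the plan says.** Section 7.1.10.2 has alcohol consumption measured with the TLFB Form 90, "administered at initial screening assessment and at 6 and 12 month follow-up after initiation of acamprosate". The same paragraph says that "time to first alcoholic drink, relapse to any drinking and relapse to heavy drinking" will be computed. The TLFB row of Table 1 (section 7.1.10) agrees: it lists "Time to first alcoholic drink Time to relapse to any drinking Time to relapse to heavy drinking" and is ticked at baseline, month 6 and month 12, but not at the bi-monthly visits of months 1 to 6.

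The look-back length appears only in the summary (section 1). There, total consumption, drinks per drinking day and percent days abstinent are measured "in the previous 90 days derived using the Time Line Follow Back Form 90". The next sentence reads "Time to first drink, relapse to any drinking and relapse to heavy drinking (8+/6+ UK units for males/females on a single occasion) derived from self-report", with no window and no named instrument.

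Section 7.1.1 sets the visit times: "Follow-up contacts with the research team will take place 6 (+30 days) and 12 (+60 days) months post randomisation". Section 7.2.4 gives the analysis: "Time to relapse and relapse to heavy drinking will be assessed using survival analysis".

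The bi-monthly visits are described as collecting adherence data and reasons for non-adherence, and in addition "Participants will be asked at each bi-monthly research visit whether they have experienced any side effects from the medication". No drinking item is named for them.

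**The concern.** Participants must be abstinent at entry, so a first drink can occur from day 0. An outcome measured as time since randomisation needs drinking information that runs without a break from that day. The text ties three such outcomes to a form that the summary describes as covering 90 days, given twice after baseline at visits six months apart. On that reading the first window opens about three months after randomisation, and a second gap follows the month-6 visit.

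Two things can go wrong for a first event in a gap. If drinking continues or recurs inside the next window, the event is dated to the first drinking recorded there, which is too late. If abstinence was regained before the window opened, the participant is recorded as event-free for that period.

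This bears on a secondary hypothesis in section 6, which names latency to first drink and both kinds of relapse at 6 and 12 months and relates them to adherence. Adherence is measured over 24 weeks (168 days) from randomisation, so on the 90-day reading drinking would go unrecorded for roughly the first 92 of those days. The weekly and fortnightly medication-management calls (6 + 6 = 12 weeks, or 84 days) fall wholly inside that first gap. Section 5.2 itself cites an analysis in which early non-adherence went with poorer alcohol outcomes than late non-adherence.

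**Working it through.** The protocol states no event count, relapse distribution or power for these outcomes, so there is no figure of its own to reproduce. The 524 analysed and 748 allocated in section 7.2.2 are derived for adherence and do not enter here.

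**Days covered, if the look-back is 90 days**

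- Visits on time, at about days 182.5 and 365. The windows open at 182.5 − 90 = 92.5 and 365 − 90 = 275. Uncovered: days 0 to 92.5 and 182.5 to 275, which is 92.5 + 92.5 = 185 of 365 days = 51%.
- Visits at the late limits (+30 and +60 days), at about days 212 and 425. The windows open at 212 − 90 = 122 and 425 − 90 = 335. Uncovered: 122 + 123 = 245 of 425 days = 58%.

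**Share of first events that fall in the uncovered days**

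This needs a relapse-time distribution, which the protocol does not give. The only rate in the document is in section 5, where up to 70% relapse in the 12 months after treatment. The following are assumptions: that rate applied from randomisation, with 50% and 90% as alternatives, and a Weibull time to first event, S(t) = (1 − F)^((t/365)^k), where F is the 12-month incidence and k the shape. k = 1 is a constant hazard, k < 1 a falling hazard and k > 1 a rising hazard.

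With F = 0.70, k = 1 and visits on time:

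- S(92.5) = 0.3^(92.5/365) = 0.737, so the first gap holds (1 − 0.737)/0.70 = 0.376 of first events.
- S(182.5) = 0.548 and S(275) = 0.404, so the second gap holds (0.548 − 0.404)/0.70 = 0.206.
- Together: 0.376 + 0.206 = 0.58.
- For the month-6 data alone: (1 − 0.737)/(1 − 0.548) = 0.58 fall before the window opens.

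Percentage of 12-month first events in the uncovered days, visits on time:

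| 12-month incidence | k = 0.5 | 0.75 | 1 | 1.25 | 1.5 | 2 |
|---|---|---|---|---|---|---|
| 50% | 72 | 62 | 55 | 50 | 46 | 42 |
| 70% | 76 | 66 | 58 | 53 | 49 | 44 |
| 90% | 83 | 73 | 65 | 58 | 53 | 48 |

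The range is 42% to 83%. With both visits at their late limits, 70% incidence and constant hazard give 66%.

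One result does not depend on the Weibull form. With visits on time, each gap comes before a window of nearly equal length. Any event density that does not rise over time therefore puts at least 185/365 = 51% of first events in the gaps.

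**Time origin**

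Sections 1, 6 and 7.1.1 count follow-up from randomisation. Section 7.1.10.2 counts the TLFB visits from the start of acamprosate. Section 1 allows randomisation up to one month after that start, so time zero, and the position of each window relative to it, can differ by up to about a month.

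**The case against.** The strongest reply is that the text does not fix a 90-day look-back for these outcomes. In the summary the 90 days belong to the sentence on consumption. The time-to-event outcomes come in a separate sentence that says only that they are self-reported. Section 7.1.10.2 and Table 1 name the instrument without stating how far back it asks. A question on the date of the first drink, put in the same interview, is not excluded. This stands as far as it goes: a reader might infer that months 0 to 3 and 6 to 9 are certain never to be observed, and the documents do not settle that. It does not remove the point. The TLFB is itself self-report, both detailed sections assign the outcomes to it, and no other drinking item is scheduled.

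A second reply is that the size rests on assumptions. The 70% is an upper background figure, counted from the end of treatment and not specific to this population, and the hazard shape is unknown. This also stands. A reader might infer that most relapses will be misdated or missed, but with a steeply rising hazard the share falls below half.

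A third reply is that section 7.2.4 says only survival analysis, which includes interval-censored methods, and leaves the detail to a later analysis plan. That is fair about the choice of model. It is also fair that all arms share one visit schedule, and no direction or size of bias between arms has been shown. A reader might infer biased hazard ratios from a standard analysis, but the protocol fixes neither that analysis nor that estimate. An analysis plan cannot, however, supply answers to questions that were never asked. Without information on the gap, someone abstinent throughout the window may have had a first drink before it or not yet at all.

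On the time origin, a reader might infer that every other section counts from randomisation. Several simply say 6- or 12-month follow-up without naming an origin.

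**Conclusion.** The point holds in conditional form. The protocol ties three time-to-event outcomes to a form given at months 6 and 12. The only look-back it states is 90 days, attached to other outcomes, and it schedules nothing else that would date a first drink. If the 90 days apply, 51% of the year is uncovered with visits on time and 58% with both at their late limits. The share of first events affected is 58% at an assumed 70% incidence and constant hazard, and about 42% to 83% over incidences of 50% to 90% and Weibull shapes of 0.5 to 2. It is about half or more unless the hazard rises over time.

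The primary adherence outcome, its analysis and the sample size are untouched. Percent days abstinent and units per drinking day remain valid for their 90 days. This is a should-fix: it concerns secondary outcomes, but the gap lies in data collection and is best closed before follow-up interviews take place.

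**What to change.** - Reconcile section 1, Table 1 and section 7.1.10.2 on the look-back for time to first drink and the two relapse outcomes.
- At month 6, take the calendar back to randomisation, or ask for the dates of the first drink and the first heavy-drinking day since randomisation. At month 12, go back to the previous assessment.
- Alternatively, ask for these dates at the existing bi-monthly visits as well. Those visits cover months 1 to 6 only, so the month-12 question is still needed.
- Keep the 90-day window for percent days abstinent and units per drinking day.
- Treat events known only to within an interval as interval-censored.
- In section 7.1.10.2, replace the start of acamprosate with randomisation as the time origin, in line with sections 1, 6 and 7.1.1.

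The cost is a change to the protocol and data-capture wording, some extra interview time at visits already planned, and longer recall with the less exact dates that this brings. The bi-monthly option shortens recall in the first six months.

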Process outcome measures: Participants' beliefs about medications (BMQ; measured at baseline and 6 month follow-up), the therapeutic relationship with the care provider (STAR: measured at 6 month follow-up) adverse events (measured at each bi-monthly research visit).

Economic outcome measures: Health related quality of life (EQ-5D-5L) and Adult Service Use Schedule modified for alcohol-misusing populations measured at baseline, 6 and 12 months post-randomisation. Costs associated with the provision of control and trial interventions, including costs associated with delivery, training, management and overheads.

**Primary analysis:** The primary analysis will be conducted using an intention-to-treat approach. As the study involves three arms, the initial step of the primary analysis will use a multiple analysis of covariance, adjusted for stratification factors, to explore for overall effects between the three arms. If evidence of effect is observed a second analysis, using an analysis of covariance, will explore the mean differences in the primary outcome by comparing SS versus SS+MM and SS versus SS+MM+CM. All results will be presented with estimates of precision and associated 95% confidence intervals.

**Economic analysis:** Analysis of the costs and effects of MM with or without CM for alcohol dependence compared to SS. The primary economic perspective will be the health and social care provider perspective. Broader perspectives will be considered in sensitivity analyses (i.e. criminal justice contacts and criminal activity, patient and family costs).

**Sample size:** Differential allocation of the order of 2:1:1 to maximize the utility of resources with twice as many being allocated to the SS group than the intervention groups. A clinically important difference in adherence to medication is estimated as an effect size of the order of 0.3. To estimate this difference using power of 80%, alpha 0.05 with a 2 sided test requires 524 analysed at 6 months post-randomisation across the three groups. Allowing for attrition of 30%, less than observed in other trials in similar populations, requires a total sample size at allocation of 748; 374 allocated to SS, and 187 each to SS+MM and SS+MM+CM. In addition to addressing the primary outcome the sample size is sufficient to identify a clinically important difference effect size of 0.3 for alcohol consumption measures at both 6 and 12 months post randomization.

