## **6. Aims and objectives**

Aim:

1. To evaluate the acceptability, effectiveness and cost-effectiveness of adjunctive MM with and without CM in improving adherence to acamprosate for relapse prevention in alcohol dependence.

Objectives:

- I. To conduct an internal pilot study to assess the feasibility, recruitment and acceptability of the proposed MM and CM interventions for pharmacists and service users.
- II. To conduct a definitive three-arm, randomised controlled trial of the effectiveness of MM with and without CM compared to SS alone in enhancing adherence to acamprosate in alcohol dependence relapse prevention.
- III. To estimate the cost effectiveness of MM with and without CM compared to SS alone in enhancing adherence to acamprosate in alcohol dependence relapse prevention.
- IV. To assess the impact of adherence to acamprosate for alcohol dependence relapse prevention on abstinence and reduced alcohol consumption.

Primary effectiveness and cost-effectiveness hypotheses:

- MM and MM+CM will be more effective than SS alone in terms of the percentage of prescribed acamprosate taken, measured using the medication events monitoring system, supplemented by pill count and self-report at 6 months post-randomisation.
- MM and MM+CM will be more cost-effective than SS alone at 12 months post-randomisation.

Secondary hypotheses:

- MM and MM+CM will be more effective than SS in terms of the percentage of prescribed medication taken, measured using the medication events monitoring system, supplemented by pill count and self-report, at 12 months post-randomisation.
- Greater adherence to acamprosate will be associated with improved alcohol outcomes, namely a higher percentage of days abstinent, less units of alcohol per drinking day, longer time (latency) to first alcoholic drink, reduced relapse to any drinking and reduced relapse to heavy drinking at 6 and 12 months post-randomisation.
- Service user beliefs about medication, and therapeutic relationship with care providers, will moderate medication adherence at 6, and 12 months post-randomisation.

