#### *7.1.1.1 Treatment arm 1: Standard support (SS)*

All participants in the trial will be prescribed acamprosate (two 333mg tablets morning, afternoon and evening or two 333mg tablets in the morning and one 333mg tablet in the afternoon and evening if the service users body weight is below 60kg) as soon as possible following alcohol abstinence in addition to the psychosocial care normally provided. The decision to initiate acamprosate will be determined by the treating clinician in the specialist alcohol service in conjunction with the service user.

The NICE guideline on diagnosis, assessment and management of harmful drinking and alcohol dependence (13) recommends, "Service users taking acamprosate should stay under supervision, at least monthly, for 6 months, and at reduced but regular intervals if the drug is continued after 6 months" p426. In clinical practice, after completion of assisted alcohol withdrawal, service users remain under the care of the specialist alcohol service for up to three months before they are transferred back to the care of their GP for ongoing care including prescribing. The type, frequency and intensity of psychosocial intervention received vary between specialist alcohol services and between individual service users, dependent on their needs, local funding and services available. As this is a pragmatic RCT, SS will be the care normally provided by local participating services, and service use will be recorded for each participant. However, participating services have agreed to follow the NICE guideline with respect to acamprosate prescribing with trial participants. Based on the current service provision of the five proposed study centres, SS is monthly pick up of prescribed acamprosate from the community pharmacy and monthly monitoring of the service user for three months by the specialist alcohol service and then returned to the care of their GP for monthly monitoring in accordance with the NICE guidelines (13) and current NHS clinical practice. As the trial is pragmatic it will be possible for patients to continue being prescribed acamprosate beyond the 24 week period of medication adherence monitoring providing this is agreed between patients and clinicians, in accordance with NICE guidelines.

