MM will provide support in developing strategies to help participants to manage their medication including the rationale for taking acamprosate, adhering to the dose regimen and managing side effects, education about their medication and alcohol dependence, and supporting participants' efforts to change their drinking behaviours. Treatment goals will be identified to tailor the intervention to the participant and an individual plan for maintaining adherence will be developed with the participant in the initial session to guide successive MM sessions. Over the 6 month period the pharmacist will send four summary letters to the participant highlighting the participant's individual aims, goals and key information regarding their medication management plan.

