## **10. Safety reporting**

A Serious Adverse Event (SAE) is defined as an untoward occurrence that;

- a. Results in death;
- b. Is life threatening
- c. Requires hospitalisation or prologation of an existing hospital stay;
- d. Results in persistent or significant disability or incapacity;
- e. Consists of a congenital anomaly or birth defect; or
- f. Is otherwise considered medically significant by the investigator.

The Chief Investigator will report an SAE to the Research Ethics Committee (REC) who provided favourable ethical opinion within 15 days of becoming aware of the event if the event is related (that is, resulted from administration of any of the research procedures), and unexpected (that is, the type of event is not listed in the protocol as an expected occurrence).

If an urgent safety measure is required, the Chief Investigator will immediately by telephone and then in writing within 3 days inform the REC who gave favourable ethical opinion the reasons for the urgent safety measures and the plan for further action.

The Chief Investigator will report on the safety of participants in annual progress report to the REC.

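### Adverse events are a named outcome, but the only harms question described covers medication side effects, and the protocol does not say how serious adverse events are found

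*Protocol*

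**What the plan says.** Section 1, under process outcome measures, includes "adverse events (measured at each bi-monthly research visit". Nothing there limits these events to the drug.

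Section 7.1.10.2 gives the only collection instruction for harms: "Participants will be asked at each bi-monthly research visit whether they have experienced any side effects from the medication". It adds that reasons for non-adherence are recorded.

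Section 7.1.10 introduces the schedule: "Table 1 outlines the study outcome measures and timing of their administration during the study". Table 1 has no row for adverse events or for side effects. The nearest entry is self-reported adherence, which includes reasons for non-adherence.

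On what is tested, section 6 states the aim: "To evaluate the acceptability, effectiveness and cost-effectiveness of adjunctive MM with and without CM in improving adherence to acamprosate". On the drug, section 7.1.1.1 says: "All participants in the trial will be prescribed acamprosate".

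Section 10 begins "A Serious Adverse Event (SAE) is defined as an untoward occurrence that" and then lists the usual seriousness criteria. Reporting to the ethics committee within 15 days applies "if the event is related (that is, resulted from administration of any of the research procedures), and unexpected". Expectedness is judged against events listed in the protocol. The section also has an urgent-safety-measure route and an annual report on participant safety. Section 4 has an independent committee review trial data at least once a year and advise on safety.

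**The concern.** The outcome is broad where it is named and narrow where its collection is described. The narrow wording asks about a treatment that every arm receives, and it requires the participant to decide first that acamprosate was the cause. A problem that a participant links to the calls or the vouchers, or to nothing in particular, is not asked about.

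If sites follow section 7.1.10.2, the adverse-event table in the final report will be a table of perceived drug side effects. That is a weak basis for any statement on the safety of MM or CM. Events that were never asked about cannot be recovered at the analysis stage, so a later analysis plan cannot repair this.

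**Working it through.** There is no figure to reproduce. The check sets the relevant sections side by side.

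| Place | What it covers | Limited to the drug? |
|---|---|---|
| Section 1, process outcomes | Adverse events, each bi-monthly visit | No |
| Section 7.1.10.2 | Side effects, each bi-monthly visit | Yes |
| Table 1 | No row for either | Not applicable |
| Section 10, definition | Serious untoward occurrences | No |
| Section 10, 15-day rule | Related to research procedures, and unexpected | No |
| Section 10, annual report | Safety of participants | No |

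**Step 1: named outcome against collection.** Section 1 and section 7.1.10.2 refer to the same visits but to different sets of events. Drug side effects are a subset of adverse events. Table 1, which is meant to set out the outcome measures, does not settle which set is intended.

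**Step 2: collection against the randomised contrast.** Acamprosate is common to all arms. The arms differ in MM and CM. A question restricted to acamprosate can show arm differences in perceived drug effects, for example if adherence rises. It cannot show events tied to MM or CM themselves.

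**Step 3: finding serious events.** Section 10 defines a serious adverse event by its consequence, whatever the cause. No section gives a question, record check or other step by which such events come to the team's notice. The described visit question reaches only those that the participant attributes to the medication. The annual report and the independent committee can use only what has been collected.

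**Step 4: expectedness.** The 15-day rule refers to a list of expected events, and the protocol contains none. Read literally, every related serious event is then unexpected and goes to the ethics committee. The rule still works, but the reference points to nothing.

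**Step 5: reach.** The wording applies to all arms, so the gap covers 374 + 187 + 187 = 748 planned participants. The number of events that would be missed cannot be estimated from the protocol.

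**The case against.** The strongest reply is that section 1 already promises adverse events at each visit, and that question wording and causality assessment usually sit in case report forms or safety procedures not shown here. This stands in part: the text shows a conflict between two sections, not a proven absence. It does not remove the point, because the protocol chose to describe the question and described it narrowly.

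A reader might infer more than the protocol supports.

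- **That harms of the interventions are never elicited.** Section 1 says otherwise. Drinking by timeline follow-back, the Alcohol Problems Questionnaire, EQ-5D-5L and the service-use schedule are collected in all arms at 6 and 12 months. They can show some harm by arm, although not as adverse events and without assessment of cause.
- **That the serious-event rule bypasses MM and CM.** MM and CM are what the research adds to usual care, so research procedures naturally include them. The relatedness condition applies only to the 15-day report. The annual safety report and committee review have no such condition.
- **That a serious acamprosate reaction after improved adherence counts as unrelated.** Section 10 does not address indirect causation. Widening the definition of related would be a preference.
- **That the expectedness test cannot be applied.** It can, as step 4 shows, and it errs towards over-reporting.
- **That event counts depend on the MM calls.** The schedule gives 6 weekly + 3 fortnightly + 3 four-weekly = 12 calls in each MM arm and none under standard support, and MM content includes "adhering to the dose regimen and managing side effects". However, no section feeds disclosures from calls into the outcome. Section 1 ties it to research visits, which all arms have. Bias by arm is therefore not shown.

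**Conclusion.** The concern holds as an inconsistency with a practical consequence. The protocol names adverse events as an outcome, describes a question confined to perceived side effects of a background drug, omits both from Table 1, and does not say how serious adverse events are identified. Followed as written, the harms outcome could not compare MM and CM with standard support.

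This rests on one assumption: that section 7.1.10.2 describes the question actually asked. If the case report form already has a broader question, the remedy reduces to correcting the text and the table. The primary outcome and the sample size are unaffected. The change is worth making because lost events cannot be recovered later and the visits already exist.

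**What to change.** 1. Reconcile section 1, section 7.1.10.2 and Table 1 so that all three describe the same outcome.
2. At each bi-monthly visit, ask one neutral question in identical words in all arms: whether there has been any new or worse health problem, hospital stay or emergency attendance since the last contact. Record attribution afterwards, as a separate item that can name acamprosate, MM, CM or none of these.
3. State in section 10 that the answers are used to identify serious adverse events. Table 1 places these visits in months 1 to 6, so also say how such events are identified after that.
4. Add a row for adverse events to Table 1.
5. In section 10, either list the expected events or state that there are none.

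The cost is one reworded item on the existing electronic form and a wording amendment. The downside is more unrelated events to record, at visits that already take place.
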